3.2 OUTCOMES QUESTIONNAIRES

Outcome measures will be completed by participants at time points indicated in Study Calendar [3.4](#) to coincide with CALM intervention session time points and take approximately 40-60 minutes to complete.

These instruments are described in Section [1.2.3](#), submitted as a separate document, and will include the following:

- The Patient-Reported Outcomes Measurement Information System (PROMIS-Depression)
- The Death and Dying Distress Scale (DADDS)
- The Quality of Life-Cancer Scale (QUAL-EC)
- The modified and brief Experiences in Close Relationships (ECR-M-16)
- Presence and severity of the symptoms (MDASI-BT or MDASI-SP)
- Health outcomes (EQ-5D)
- The Clinical Evaluation Questionnaire (CEQ)*

- The Was it Worth it Questionnaire (WIWI)*

***NOTE:** All Outcomes questionnaires will be completed at baseline, 3-month, and 6-month timepoints, except for the CEQ and WIWI which will be completed at the 3-month timepoint and if more than 3 sessions are completed, the CEQ and WIWI will also be completed at the 6-month timepoint.

A survey link will be sent out to participants for completion of study questionnaires at all time points.

The questionnaire responses will be entered by study subjects directly into the Scribe/Labmatrix system.

Those participants who do not return an assessment within 2 weeks may receive up to 2 reminder email/telephone calls from research staff.

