3.4 STUDY CALENDAR

Procedure	Baseline evaluation	CALM Therapy	3-month evaluation (+/- 2 weeks)	6-month evaluation (+/- 2 weeks)
CALM Therapy ¹			→	
Adverse Events			→	
PROMIS-Depression	X		X	X
The Quality of Life at the End of Life-Cancer Scale (QUAL-EC)	X		X	X
The Death and Dying Distress Scale (DADDS)	X		X	X
Experiences in Close Relationships (ECR-M-16)	X		X	X
Clinical Evaluation Questionnaire (CEQ) ⁵			X	X
MDASI-BT or MDASI-SP ²	X		X	
EQ-5D ²	X		X	
Qualitative Interview ^{3,4}		X		
WIWI ⁵			X	X

1. CALM therapy includes 3-6 individual sessions delivered over 6 months. Additional sessions may be offered if clinically indicated while the participant is on the study.
2. Completed within 2 months prior to CALM therapy and any time after the 3rd CALM session while the participant is on the study. If these questionnaires are completed on 16C0151 protocol within the time frames required by this protocol, completion of these questionnaires do not need to be repeated.
3. The Qualitative Interviews will be conducted and scheduled within 1-2 months after participants' 3rd session.
4. The Qualitative Interviews will be conducted on a select number of participants until data saturation is reached (i.e., estimated to be 15-30 patients).
5. The CEQ and WIWI will be completed at 3 months with 6 month completion if more than 3 sessions are completed.

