8.3.3 Exploratory Analyses

To determine the effect of the CALM intervention on well-being, we will calculate effect size differences in well-being using between baseline and months 3 and 6.

To explore the effects of the CALM intervention on symptom burden and interference, we will report subscale scores for the MDASI-BT and MDASI-SP and the proportion of participants with 5 or greater (moderate to severe) and 7 or greater (severe) ratings on the 0-10 numeric rating scale of each symptom items for each time point. To quantify the immediate CALM effect, we will calculate the effect size difference between baseline scores and month 3. To quantify the long term CALM effect, we will calculate the effect size differences between baseline and month 6. We will fit a linear mixed model with participants as a random effect and time as a fixed effect using MDASI-BT and MDASI-SP subscale scores as a dependent variable.

To explore the effects of the CALM intervention on health status, we will perform linear mixed models and effect size calculations on health status using raw and subscale scores from the EQ-5D. To quantify the immediate CALM effect, we will calculate the effect size difference between baseline scores and month 3. To quantify the long-term CALM effect, we will calculate the effect size differences between baseline and month 6. We will fit a linear mixed model with participants as a random effect and time as a fixed effect using EQ-5D as a dependent variable.

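### Calendar footnote 2 does not secure the dated month-3 and month-6 MDASI and EQ-5D forms that sections 3.2 and 8.3.3 require

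*Combined protocol and SAP*

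**What the plan says.** Section 3.2 lists the MDASI (BT or SP) and the EQ-5D among the outcome measures and states: "All Outcomes questionnaires will be completed at baseline, 3-month, and 6-month timepoints, except for the CEQ and WIWI". Neither instrument is in the exception. The same section refers to the calendar for timing ("Outcome measures will be completed by participants at time points indicated in Study Calendar") and says "A survey link will be sent out to participants for completion of study questionnaires at all time points".

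Section 8.3.3 plans, for each of the two instruments, an effect size from baseline to month 3 and another from baseline to month 6. The MDASI paragraph reads "To quantify the long term CALM effect, we will calculate the effect size differences between baseline and month 6", and the EQ-5D paragraph says the same. Section 8.3.3 also plans MDASI severity proportions at every time point, and for both instruments a mixed model with time as a fixed effect.

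Section 3.4, footnote 2, is attached to the MDASI and EQ-5D rows only. It gives their timing as "Completed within 2 months prior to CALM therapy and any time after the 3rd CALM session while the participant is on the study". It then waives repetition on this condition: "If these questionnaires are completed on 16C0151 protocol within the time frames required by this protocol". Footnote 5 of the same table does name months for two other instruments: "The CEQ and WIWI will be completed at 3 months with 6 month completion if more than 3 sessions are completed".

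**The concern.** The analysis section assumes two dated follow-up values per instrument. The footnote that governs collection of those values fixes neither their number nor their dates. A team working from the calendar could collect a single follow-up form, on any date after session 3, and be in full compliance with it. The month-6 contrasts could then have no data. The month-3 contrasts could pool forms taken at quite different distances from baseline.

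Date matters for these measures. Section 1.2.3.7 says the MDASI asks about the last 24 hours, and section 3.1 says the trial's outcomes are affected by recurrence. A form that was never collected at month 6 cannot be recovered later.

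The ambiguity also reaches a secondary objective. The compliance criterion in 8.3.2 requires at least 80% of participants to complete the outcome measures at every time point. A participant with one MDASI follow-up form passes under footnote 2 and fails under 3.2.

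**Working it through.** The plan gives no figure to reproduce on this point. The check is a comparison of passages and a count of forms.

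**Passages side by side, for MDASI and EQ-5D**

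| Source | Baseline | Follow-up |
|---|---|---|
| 2.4 | within 2 months before therapy | not covered |
| 3.2 note | required | month 3 and month 6 |
| 3.4 footnote 2 | within 2 months before therapy | after session 3, no month, no window, no number of forms |
| 8.3.3 | reference value | one contrast at month 3, one at month 6 |

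The baseline side agrees. The follow-up side does not.

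**Does the footnote's timing amount to month 3 or month 6?** No. Footnote 1 says "CALM therapy includes 3-6 individual sessions delivered over 6 months", and no date is set for session 3. If session 3 falls after the month-3 visit, a form completed at month 3 satisfies 3.2 but not footnote 2.

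**Form count**
- Needed by 3.2 and 8.3.3: 2 follow-up forms per participant per instrument.
- Enough to satisfy footnote 2: 1.
- With the 80 evaluable participants of section 8.2: 80 x 2 = 160 forms per instrument, against 80 x 1 = 80.

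**Contrast count** (MDASI-BT or MDASI-SP taken as one instrument per participant; subscales not counted separately)
- Planned: 2 instruments x 2 follow-up times = 4.
- Possible per participant with one follow-up form per instrument: at most 2 x 1 = 2 of 4.

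**Two readings of footnote 2**
- (a) It asks for one follow-up form. That form cannot supply both the month-3 and the month-6 contrast, and it is tied to neither date.
- (b) It only widens the window in which a 16C0151 form is accepted, and 3.2 still calls for two follow-ups. All 4 contrasts can then be computed, but a substituted form may come from any date after session 3 and is not held to the calendar's +/- 2 weeks.

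On neither reading are dated values at both months assured.

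**What is not relied on.** In the text as extracted, the two rows show a follow-up mark under month 3 and none under month 6. The CALM therapy and adverse-event arrows also sit only under month 3 although therapy runs over 6 months, so a lost spanning cell is plausible. The argument uses only the wording of footnote 2, 3.2 and 8.3.3.

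**The case against.** The best defence is that calendar dates come from the column heads, not the footnotes. The two rows do carry a mark in the month-3 column. PROMIS-Depression and three other scales have no footnote and are dated all the same, and footnote 5 names months only because it sets a condition. Other text also points to two follow-ups: the précis describes three collection times for the standardized measures, section 3.1 places further questionnaires at about 3 and 6 months, and 3.2 sends the survey link each time. On this view one phrase is loose and the rest of the protocol settles it.

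Much of this supports 3.2 as the likely intent, but it does not remove the conflict. The month-3 mark is the very entry that footnote 2 qualifies, and 3.2 itself sends the reader to the calendar. The objectives for the MDASI and EQ-5D in 1.1.3 name no months, although those for QUAL-EC and ECR-M-16 do, so a single follow-up may have been intended.

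A second point is fair. The reuse condition can be read as the time frames of the whole protocol, in which case 16C0151 forms would be held to the dated windows. That reading would cure the substitution problem, but the first sentence of footnote 2 would still need correcting.

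It is also right that the consequences are limited to exploratory work and one count, and that the cost of adding month-6 forms depends on whether 3.2 already requires them.

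**Conclusion.** The inconsistency is real. Sections 3.2 and 8.3.3 need two dated follow-up forms per instrument; footnote 2 can be met by one undated form. If it is followed that way, each participant can support at most 2 of the 4 planned MDASI and EQ-5D contrasts. If it is read only as a reuse rule, all 4 can be computed, but the values need not fall at month 3 or month 6.

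The size of any resulting bias cannot be stated, because the documents give neither the spacing of sessions nor how often 16C0151 forms are completed.

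The affected analyses carry no alpha, power statement or decision rule. The one criterion touched is the 80% compliance count. The primary PROMIS-Depression test, the DADDS analysis and the sample size stand. The text should be corrected, but the point does not threaten the trial's main conclusion.

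**What to change.** Reconcile 3.2, 3.4 and 8.3.3 in one of two ways, according to what the sponsor intends.

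1. **Two follow-ups.** In 3.4, mark the MDASI and EQ-5D separately at 3 and 6 months (+/- 2 weeks). Reword footnote 2 so that reused 16C0151 follow-up forms must fall in those windows. Leave the 2-month baseline window as it is.
2. **One follow-up.** Delete the month-6 MDASI and EQ-5D contrasts from 8.3.3, add both instruments to the exception in the 3.2 note, align the précis, and label the remaining contrast as post-session-3.

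In either case, state in 8.3.2 that the 80% compliance count follows the reconciled schedule.

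Option 1 costs a calendar and footnote edit, and 16C0151 forms outside the windows would have to be repeated, which gives up some of the burden relief. If only one follow-up form is now being collected, it also adds one MDASI (about 5 minutes by section 1.2.3.7) and one EQ-5D at the existing 6-month survey contact; if 3.2 is already being followed, those forms are not new. Option 2 costs text edits only, but the long-term contrast for these two instruments is lost.

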1.1.3 Exploratory Objectives

- To determine the effects of the CALM intervention on psychological well-being as measured by the Quality of Life Cancer scale (QUAL-EC) and the modified and brief Experiences in Close Relationships (ECR-M-16) questionnaire at both 3 and 6 months, compared to baseline
- To explore the effects of the CALM intervention, more specifically the relationship between distress and symptom burden as measured by the M.D. Anderson Symptom Inventory-Brain tumor (MDASI-BT) for those with brain or brain and spine tumors and the M.D. Anderson Symptom Inventory-Spine Tumor (MDASI-SP) for those with spine tumors, symptom severity and symptom factor scores.
- To explore the effects of the CALM intervention on the relationship between distress and symptom interference as measured by the MDASI-BT or MDASI-SP interference scores.
- To explore the effects of the CALM intervention on health status as measured by the EQ-5D.

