2.4 BASELINE EVALUATION

Baseline evaluation will be completed within 14 days prior to CALM therapy initiation unless specified otherwise.

Participants will be asked to complete 6 questionnaires at baseline:

1. PROMIS-Depression,
2. Quality of life (QUAL-EC),
3. Death anxiety (DADDS),
4. Attachment Insecurities (ECR-M-16),
5. Presence and severity of the symptoms (MDASI-BT or MDASI-SP) (within 2 months prior to CALM therapy),
6. Health outcomes (EQ-5D) (within 2 months prior to CALM therapy).

For more details, please, see Section [3.2](#)

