8 STATISTICAL CONSIDERATIONS

8.1 STATISTICAL HYPOTHESIS

Primary Endpoint:

- To demonstrate the effects of the CALM intervention in the reduction of depressive symptoms using the PROMIS-Depression scale in PCNST participants from baseline to 6 months.

Secondary Endpoints:

- To demonstrate the short-term effects of the CALM intervention in the reduction of depressive symptoms using the PROMIS-Depression scale in PCNST participants from baseline to 3 months.
- To determine the effects of the CALM intervention on death anxiety using the Death and Dying Distress Scale at both 3 and 6 months, compared to baseline.
- To describe the feasibility of implementing CALM remotely in a sample of PCNST participants.

Exploratory Objectives:

- To determine the effects of the CALM intervention on psychological well-being as measured by the Quality of Life Cancer Scale (QUAL-EC) and the modified brief Experiences in Close Relationships (ECR-M-16) questionnaire at both 3 and 6 months, compared to baseline
- To explore the effects of the CALM intervention, more specifically the relationship between distress and symptom burden as measured by the M.D. Anderson Symptom Inventory-Brain tumor (MDASI-BT) or M.D. Anderson Symptom Inventory-Spine Tumor (MDASI-SP) symptom severity and symptom factor scores.
- To explore the effects of the CALM intervention on the relationship between distress and symptom interference as measured by the MDASI-BT or MDASI-SP interference scores.

To explore the effects of the CALM intervention on health status as measured by the EQ-5D and CEQ.

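### Two exploratory objectives concern how distress relates to MDASI symptom burden and interference, but Section 8.3.3 plans no analysis that estimates either association

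*Combined protocol and SAP*

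**What the plan says.** Two of the four exploratory objectives in Section 1.1.3 are worded as relationships. One concerns "the relationship between distress and symptom burden as measured by the M.D. Anderson Symptom Inventory-Brain tumor (MDASI-BT" (or the MDASI-SP for spine tumors), using severity and factor scores. The other concerns "the relationship between distress and symptom interference as measured by the MDASI-BT or MDASI-SP interference scores". Section 8.1 repeats both; the second begins "To explore the effects of the CALM intervention on the relationship between distress and symptom interference".

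In Section 8.3.3 the aim loses its reference to distress: "To explore the effects of the CALM intervention on symptom burden and interference, we will report subscale scores". The section then lists four analyses:

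- MDASI subscale scores;
- for each symptom item and time point, the proportions rated 5 or more and 7 or more;
- effect sizes from baseline to month 3 and from baseline to month 6;
- a linear mixed model with participant as a random effect and "time as a fixed effect using MDASI-BT and MDASI-SP subscale scores as a dependent variable".

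Section 8.3.3 does not say which instrument measures distress. Section 1.2.1 reports distress from the MDASI-SP and, separately, anxiety and depression from PROMIS instruments. Section 2.4 allows the baseline MDASI "within 2 months prior to CALM therapy", whereas PROMIS-Depression falls under the general 14-day baseline window.

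**The concern.** An objective about a relationship needs an analysis with both variables in it. The planned MDASI analyses ask whether symptom scores change over time. That is a reasonable question, but not the one these two objectives pose.

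The relationship is also part of the trial's rationale. Section 1.2.1 counts the physical burden of disease among the most prominent contributors to distress, and the first CALM domain is symptom management. Section 1.2.2 says the results will feed the design of a randomized study. If the analysis is improvised after the data are seen, there are several candidate distress measures to cross with severity, factor and interference scores, and nothing fixes the choice.

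**Working it through.** **1. Objectives against analyses.**

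| Planned MDASI analysis (8.3.3) | What it estimates | Distress–MDASI association? |
|---|---|---|
| Subscale scores by time | MDASI level | No |
| Item proportions at 5+ and 7+ | Prevalence, item by item | No |
| Effect sizes to months 3 and 6 | MDASI change | No |
| Mixed model, time fixed, participant random | Mean MDASI change | No |

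Sections 8.3.1 and 8.3.2 analyze PROMIS-Depression, the DADDS and feasibility. Neither relates any of these to the MDASI.

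**2. What the planned model can see.** The planned model is MDASI = intercept + time + participant effect + error. None of its parameters is an association with distress, or a change in one over time. A small simulation illustrates this. The assumptions, which are not from the documents, are: 80 participants, two occasions, MDASI SD 2, intraclass correlation 0.5, mean change −0.5, distress SD 2, and 150 replicates per row.

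| True distress–MDASI correlation | Time effect, planned model (SE) | Distress slope once distress and time × distress are added (SE) |
|---|---|---|
| 0 | −0.52 (0.22) | −0.02 (0.10) |
| 0.3 | −0.49 (0.22) | 0.31 (0.10) |
| 0.6 | −0.52 (0.22) | 0.61 (0.08) |

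The planned model gives essentially the same output whether the association is absent or strong.

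**3. The plan's own figure.** The only sample size is for the primary paired test (Section 8.2): mean reduction 1.8, SD of the difference 5.7, two-sided 5%, power 80%. The normal formula gives ((1.960 + 0.842) × 5.7/1.8)² = 78.7, so 79. The exact t calculation gives 80.6, so 81, and power at 80 is 79.7%. The stated 80 is reproduced closely, and 80/(1 − 0.20) = 100. No figure is given for the MDASI objectives.

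**4. Precision of a correlation.** The correlation detectable with 80% power at two-sided 5% is tanh(2.80/√(n − 3)). The 95% CI around an observed 0.30 is tanh(atanh 0.30 ± 1.96/√(n − 3)), with atanh 0.30 = 0.3095. The brain/spine split is not stated, so two splits of 80 are assumed.

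| n | 2.80/√(n − 3) | Detectable r | 95% CI if r = 0.30 |
|---|---|---|---|
| 80, pooled | 0.319 | 0.31 | 0.09 to 0.49 |
| 65, brain | 0.356 | 0.34 | 0.06 to 0.51 |
| 15, spine | 0.809 | 0.67 | −0.25 to 0.70 |
| 60, brain | 0.371 | 0.35 | 0.05 to 0.52 |
| 20, spine | 0.680 | 0.59 | −0.16 to 0.66 |

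The pooled row is a best case. The 80 counts participants evaluable for PROMIS-Depression at 6 months, not paired MDASI and distress forms.

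**5. Timing.** Section 3.2 has all outcome questionnaires except the CEQ and WIWI at baseline, 3 and 6 months. The calendar in Section 3.4 marks the MDASI at baseline and 3 months only, and its footnote allows the follow-up form at any time after the third session while on study. Section 8.3.3 assumes a month 6 value. On the calendar's schedule there are two MDASI occasions, and a follow-up form may lie well away from the nearest PROMIS form. Recall differs too: 24 hours for the MDASI (1.2.3.7) and 7 days for PROMIS-Depression (1.2.3.1).

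**The case against.** The strongest reply is that these are exploratory objectives, loosely worded, in a single-arm study. The first starts from the effects of CALM and only then narrows to a relationship. Section 8.3.3 restates the aim as effects on burden and interference, which may be what the sponsor meant, and an association could be added later from the stored data. This stands as a reason to rate the point as minor and to accept rewording as a full remedy. It does not remove the mismatch, because Section 8.1, within the statistical chapter, keeps the relationship wording.

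Four stronger readings are tempting, and the documents do not support them:

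- **That distress is absent from every planned analysis.** Section 1.2.1 reports distress from the MDASI-SP, so the item-by-item proportions would describe at least that item. PROMIS-Depression and the DADDS are analyzed in their own right. What is missing is an association.
- **That distress means PROMIS-Depression.** The documents do not define it for these objectives, and Section 1.2.1 distinguishes it from depression. PROMIS-Depression is a sensible candidate, not the stated one.
- **That the answer is available with the precision of 80 pairs.** Separate brain and spine analyses are smaller, and the forms may not be close in time.
- **That a fuller model would show CALM changing the relationship.** With two occasions, splitting distress into between-person and within-person parts and interacting both with time asks too much of the data: each within-person deviation is just plus or minus half the change score. With no comparator, a changed relationship cannot be attributed to CALM.

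**Conclusion.** The mismatch is real and can be read directly from the text: two of four exploratory objectives have no corresponding estimate. It rests on no numerical assumption; the simulation only illustrates it. Severity is minor. The primary test, the sample size, the stopping boundary and participant safety are unaffected.

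If the association is added, it will be descriptive and imprecise. Only moderate correlations (about 0.31 to 0.35) would be detectable in the pooled or brain group, and only large ones (about 0.59 to 0.67) in the spine group. These figures assume 80 usable pairs and the splits shown above.

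**What to change.** In Section 8.3.3, before analysis:

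1. Name the distress measure, for example PROMIS-Depression with the DADDS as a second measure.
2. For MDASI severity (and factor) and interference scores, add one simple analysis: either distress and time × distress terms in the existing mixed model, or baseline and change-score correlations with 95% CIs.
3. Analyze the MDASI-BT and MDASI-SP separately, and pair forms by actual assessment date.
4. Leave overlapping MDASI items (any distress item, and the mood interference item listed in Section 1.2.3.7) out of the score being related to distress, so that a measure is not correlated with itself.
5. Report the result as a descriptive association, not as an effect of CALM.
6. Reconcile Sections 3.2, 3.4 and 8.3.3 on when the MDASI is collected.

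If the association is not wanted, reword the two objectives in Sections 1.1.3 and 8.1 to match the time-only analysis; item 6 is needed either way. The cost is SAP wording and a little modeling. The association analysis uses instruments already in the plan.
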